6.5 Assessment of Subject Compliance with Study Intervention/Investigational Product

Study product will be administered to subjects by an unblinded study vaccine administrator via IM injection at all dosing times according to subject treatment assignment and as described in Section 6.2. Thus, subject compliance is not anticipated to be an issue. Deviations from the dose schedule may only occur as described in Section 6.3.

6.6 Concomitant Medications/Treatments

Administration of any medications, therapies, or vaccines will be recorded on the appropriate data collection form. Concomitant medications will include all current medications and medications taken within 60 days prior to signing the informed consent form through approximately 28 days after the last study vaccination or through the early termination visit (if prior to 28 days after the last study vaccination), whichever occurs first. Medications reported in the electronic case report form (eCRF) are limited to those taken within 30 days prior to the first study vaccination through approximately 28 days after the last study vaccination. Prescription and over-the-counter drugs will be included as well as herbals, vitamins and supplements. In addition, receipt of non-study influenza vaccines will be solicited through approximately 28 days after the last study vaccination, and reported in the eCRF.

Use of new medication should prompt evaluation for the presence of a new diagnosis of chronic medical disease or condition.

Medications that might interfere with the evaluation of the investigational product(s) should not be used during the study-reporting period (approximately 12 months after the last study vaccination) unless clinically indicated as part of the subject's health care. Medications in this category include the prohibited medications per the Subject Exclusion Criteria (see Section 5.1.2). In addition, the site principal investigator or appropriate sub-investigator may identify

other medications that should not be used due to a risk to subject safety or assessment of reactogenicity and immunogenicity.

7 STUDY SCHEDULE

Complete study schedule details listed by type of visit are described below. Refer also to Sections 4 and 8 and Appendix B.

7.1 Screening and Enrollment Visits

7.1.1 Visit 00, Day -7, Screening, Clinic Visit, All Subjects (Window: Day -14 to Day -5 prior to first study vaccination)

Potential subjects will be screened for eligibility up to 14 days, but no less than 5 days prior to the administration of the first study vaccination. The following activities will be performed:

- Subjects will be provided with a description of this study (purpose and study procedures) and asked to read and sign the informed consent form. The informed consent form will be signed prior to performing any study procedures, including any screening procedures.
- Demographic information will be obtained by interview of subjects.
- Eligibility criteria will be reviewed with subjects.
- Complete medical history will be obtained by interview of subjects to ensure eligibility.
- All concomitant medications taken within 60 days prior to signing the informed consent form will be reviewed with subjects. Medications reported in the eCRF are limited to those taken within 30 days prior to the first study vaccination.
- Subject receipt of licensed seasonal influenza vaccines over the previous two seasons, what type (inactivated or live attenuated), and approximate date of vaccination will be recorded on the appropriate data collection form, if known. Prior receipt of licensed seasonal influenza vaccine is not exclusionary, as long as it has been administered within the allowable window (see Section 5.1.2).
- Vital signs, including oral temperature, pulse, and blood pressure, will be obtained to ensure eligibility. Subjects must not eat or drink anything hot or cold, or smoke within 10 minutes prior to taking oral temperature.
- A targeted physical examination, including an assessment for signs suggestive of a potentially immune-mediated medical condition, may be performed, if indicated based on

review of complete medical history, by a study clinician licensed to make medical diagnoses and listed on the Form FDA 1572 as the site principal investigator or sub-investigator.

- A urine or serum pregnancy test will be performed on all women of childbearing potential and must be negative to ensure eligibility.
- Approximately 4 mL of venous blood will be collected for ESR, and performed locally by the site. The ESR value must be confirmed as less than 30 mm per hour prior to randomization and first study vaccination. The ESR, if initially elevated, may be repeated once to determine eligibility.
- Approximately 90 mL of venous blood will be collected for baseline cytokine and chemokine levels and systems biology studies.
- Approximately 20 mL of urine will be collected for future research.

7.1.2 Visit 01, Day 1, Enrollment and First Study Vaccination (Dose 1), Clinic Visit, All Subjects

- Subject's willingness to participate will be reconfirmed and documented in the subject's study records prior to performing any further study procedures, including administration of the first study vaccination.
- Eligibility criteria, including results of the ESR evaluation, will be reviewed with subjects prior to the first study vaccination to ensure continued eligibility.
- Complete medical history and any updates obtained by interview of subjects since the screening visit will be reviewed with subjects prior to the first study vaccination to ensure continued eligibility.
- All concomitant medications will be reviewed with subjects prior to the first study vaccination for accuracy and completeness. Any new concomitant medications taken since the screening visit will be reviewed with subjects and assessed for continued eligibility prior to the first study vaccination. Medications reported in the eCRF are limited to those taken within 30 days prior to the first study vaccination.
- Vital signs, including oral temperature, pulse, and blood pressure, will be obtained prior to the first study vaccination. Vital signs assessed on Day 1 prior to the first study

vaccination will be considered as baseline. Subjects must not eat or drink anything hot or cold, or smoke within 10 minutes prior to taking oral temperature.

- Height and weight will be collected prior to the first study vaccination for the calculation of Body Mass Index (BMI).
- A targeted physical examination, including an assessment for signs suggestive of a potentially immune-mediated medical condition, may be performed prior to the first study vaccination, if indicated based on review of complete medical history and any updates obtained by interview of subjects since the screening visit, by a study clinician licensed to make medical diagnoses and listed on the Form FDA 1572 as the site principal investigator or sub-investigator.
- A urine or serum pregnancy test will be performed within 24 hours prior to the first study vaccination on all women of childbearing potential. Results must be negative and known prior to randomization and first study vaccination.
- Approximately 10 mL of venous blood will be collected immediately prior to the first study vaccination for baseline HAI and Neut antibody assays.
- Approximately 90 mL of venous blood will be collected immediately prior to the first study vaccination for baseline cytokine and chemokine levels and systems biology studies.
- Approximately 20 mL of urine will be collected prior to the first study vaccination for future research.
- Subjects will be enrolled in AdvantageEDCSM and assigned randomly to a treatment arm prior to the first study vaccination.
- Pre-administration reactogenicity assessments will be performed prior to the first study vaccination to establish baseline. Subjects will then receive a single dose of study vaccine via IM injection into the deltoid muscle of the preferred arm. The site of injection (right or left arm) and time of administration will be recorded on the appropriate data collection form. Subjects will be observed in the clinic for at least 20 minutes after the first study vaccination. The first study vaccination site will be examined, post-administration reactogenicity assessments will be performed, and any AE/SAEs will be recorded on the appropriate data collection form prior to discharge from the clinic.

- Subjects will be provided with a memory aid and other study-related materials to record daily oral temperature, solicited injection site and systemic reactions, any unsolicited AEs, and concomitant medications. Subjects will be encouraged to take their oral temperature around the same time each day. Subjects must not eat or drink anything hot or cold, or smoke within 10 minutes prior to taking oral temperature. Subjects will be instructed on how to use their memory aid and how to measure and record AEs prior to discharge from the clinic. Subjects will be instructed to notify the study center if they develop any severe reactions after the first study vaccination. If the site principal investigator or appropriate sub-investigator deems the reaction severe enough, further instructions will be given to the subject on the proper course of action, including a return to the clinic for immediate evaluation if appropriate.

7.2 Follow-up Visits

Follow-up visits are scheduled in reference to study vaccination dates as indicated for each visit window.

7.2.1 Visit 02, Day 2, Clinic Visit, All Subjects (Window: Day 2+1 day post first study vaccination)

- Interim medical history, including an assessment for new medical conditions and symptoms suggestive of a potentially immune-mediated medical condition, will be obtained by interview of subjects and any changes since the previous clinic visit or contact will be noted.
- Memory aid information will be reviewed with subjects.
- All concomitant medications (including solicitation for receipt of any non-study influenza vaccines) will be recorded on the appropriate data collection form.
- All AE/SAEs will be recorded on the appropriate data collection form.
- A targeted physical examination, including an assessment for signs suggestive of a potentially immune-mediated medical condition, may be performed, if indicated based on review of interim medical history, by a study clinician licensed to make medical diagnoses and listed on the Form FDA 1572 as the site principal investigator or sub-investigator.
- The first study vaccination site will be examined.

- Approximately 90 mL of venous blood will be collected for cytokine and chemokine levels and systems biology studies.
- Approximately 20 mL of urine will be collected for future research.

7.2.2 Visit 03, Day 4, Clinic Visit, All Subjects (Window: Day 4+1 day post first study vaccination)

- Interim medical history, including an assessment for new medical conditions and symptoms suggestive of a potentially immune-mediated medical condition, will be obtained by interview of subjects and any changes since the previous clinic visit or contact will be noted.
- Memory aid information will be reviewed with subjects.
- All concomitant medications (including solicitation for receipt of any non-study influenza vaccines) will be recorded on the appropriate data collection form.
- All AE/SAEs will be recorded on the appropriate data collection form.
- A targeted physical examination, including an assessment for signs suggestive of a potentially immune-mediated medical condition, may be performed, if indicated based on review of interim medical history, by a study clinician licensed to make medical diagnoses and listed on the Form FDA 1572 as the site principal investigator or sub-investigator.
- The first study vaccination site will be examined.
- Approximately 90 mL of venous blood will be collected for cytokine and chemokine levels and systems biology studies.
- Approximately 20 mL of urine will be collected for future research.

7.2.3 Visit 04, Day 8, Clinic Visit, A/H3N2v-vaccinated subjects only (Window: Day 8+2 days post first study vaccination)

- Interim medical history, including an assessment for new medical conditions and symptoms suggestive of a potentially immune-mediated medical condition, will be obtained by interview of subjects and any changes since the previous clinic visit or contact will be noted.

-
- Memory aid information will be reviewed with subjects.
 - All concomitant medications (including solicitation for receipt of any non-study influenza vaccines) will be recorded on the appropriate data collection form.
 - All AE/SAEs will be recorded on the appropriate data collection form.
 - A targeted physical examination, including an assessment for signs suggestive of a potentially immune-mediated medical condition, may be performed, if indicated based on review of interim medical history, by a study clinician licensed to make medical diagnoses and listed on the Form FDA 1572 as the site principal investigator or sub-investigator.
 - The first study vaccination site will be examined.
 - Approximately 90 mL of venous blood will be collected for cytokine and chemokine levels and systems biology studies.
 - Approximately 20 mL of urine will be collected for future research.

**7.2.4 Visit 04, Day 8, Phone Call/Electronic Communication, A/H7N9-vaccinated subjects only
(Window: Day 8±2 days post first study vaccination)**

Study personnel will contact subjects by phone or electronic communication (e.g., email, text message) to solicit any AE/SAE and concomitant medication information (including solicitation for receipt of any non-study influenza vaccines) and review information on their memory aid.

**7.2.5 Visit 05, Day 29, *Second Study Vaccination (Dose 2) for A/H7N9-vaccinated subjects only, Clinic Visit, All Subjects
(Window: Day 29±2 days post first study vaccination)**

***This visit is for all subjects; however only A/H7N9-vaccinated subjects will receive the second study vaccination (Dose 2).**

- A/H7N9-vaccinated subjects only – Eligibility criteria, will be reviewed with subjects prior to the second study vaccination* to ensure continued eligibility.
- Interim medical history, including an assessment for new medical conditions and symptoms suggestive of a potentially immune-mediated medical condition, will be

obtained by interview of subjects (prior to the second study vaccination*) and note any changes since the previous clinic visit or contact will be noted.

- All concomitant medications (including solicitation for receipt of any non-study influenza vaccines) will be recorded on the appropriate data collection form (prior to the second study vaccination*).
- All AE/SAEs will be recorded on the appropriate data collection form (prior to the second study vaccination*).
- Vital signs, including oral temperature, pulse, and blood pressure, will be obtained prior to the second study vaccination*. Subjects must not eat or drink anything hot or cold, or smoke within 10 minutes prior to taking oral temperature. Note: Vital signs are not required for A/H3N2v-vaccinated subjects or A/H7N9-vaccinated subjects who are discontinued from receipt of the second study vaccination and are being followed for safety.
- A targeted physical examination, including an assessment for signs suggestive of a potentially immune-mediated medical condition, may be performed (prior to the second study vaccination*), if indicated based on review of interim medical history, by a study clinician licensed to make medical diagnoses and listed on the Form FDA 1572 as the site principal investigator or sub-investigator.
- A/H7N9-vaccinated subjects only – A urine or serum pregnancy test will be performed within 24 hours prior to the second study vaccination* on all women of childbearing potential. Results must be negative and known prior the second study vaccination*.
- Approximately 10 mL of venous blood will be collected for HAI and Neut antibody assays on all subjects. A/H7N9-vaccinated subjects only – Blood should be collected immediately prior to the second study vaccination*.
- A/H7N9-vaccinated subjects only – Approximately 90 mL of venous blood will be collected immediately prior to the second study vaccination* for cytokine and chemokine levels and systems biology studies.
- A/H7N9-vaccinated subjects only - Approximately 20 mL of urine will be collected (prior to the second study vaccination*) for future research.
- A/H7N9-vaccinated subjects only – Pre-administration reactogenicity assessments will be performed prior to the second study vaccination* to establish baseline. Subjects will then

receive a single dose of study vaccine via IM injection into the deltoid muscle of the preferred arm. The second study vaccination may be given in the same preferred arm as long as there is no interference with the reactogenicity assessment. The site of injection (right or left arm) and time of administration will be recorded on the appropriate data collection form. Subjects will be observed in the clinic for at least 20 minutes after the second study vaccination. The second study vaccination site will be examined, post-administration reactogenicity assessments will be performed, and any AE/SAEs will be recorded on the appropriate data collection form prior to discharge from the clinic.

- A/H7N9-vaccinated subjects only – Subjects will be provided with a memory aid and other study-related materials to record daily oral temperature, solicited injection site and systemic reactions, any unsolicited AEs, and concomitant medications. Subjects will be encouraged to take their oral temperature around the same time each day. Subjects must not eat or drink anything hot or cold, or smoke within 10 minutes prior to taking oral temperature. Subjects will be instructed on how to use their memory aid and how to measure and record AEs prior to discharge from the clinic. Subjects will be instructed to notify the study center if they develop any severe reactions after the second study vaccination. If the site principal investigator or appropriate sub-investigator deems the reaction severe enough, further instructions will be given to the subject on the proper course of action, including a return to the clinic for immediate evaluation if appropriate.

Note: This will be the last visit for those randomized to the A/H3N2v arm.

7.2.6 Visit 06, Day 30, Clinic Visit, A/H7N9-vaccinated subjects only (Window: Day 2+1 day post second study vaccination)

- Interim medical history, including an assessment for new medical conditions and symptoms suggestive of a potentially immune-mediated medical condition, will be obtained by interview of subjects and any changes since the previous clinic visit or contact will be noted.
- Memory aid information will be reviewed with subjects.
- All concomitant medications (including solicitation for receipt of any non-study influenza vaccines) will be recorded on the appropriate data collection form.
- All AE/SAEs will be recorded on the appropriate data collection form.
- A targeted physical examination, including an assessment for signs suggestive of a potentially immune-mediated medical condition, may be performed, if indicated based on

review of interim medical history, by a study clinician licensed to make medical diagnoses and listed on the Form FDA 1572 as the site principal investigator or sub-investigator.

- The second study vaccination site will be examined.
- Approximately 90 mL of venous blood will be collected for cytokine and chemokine levels and systems biology studies.
- Approximately 20 mL of urine will be collected for future research.

**7.2.7 Visit 07, Day 32, Clinic Visit, A/H7N9-vaccinated subjects only
(Window: Day 4+1 day post second study vaccination)**

- Interim medical history, including an assessment for new medical conditions and symptoms suggestive of a potentially immune-mediated medical condition, will be obtained by interview of subjects and any changes since the previous clinic visit or contact will be noted.
- Memory aid information will be reviewed with subjects.
- All concomitant medications (including solicitation for receipt of any non-study influenza vaccines) will be recorded on the appropriate data collection form.
- All AE/SAEs will be recorded on the appropriate data collection form.
- A targeted physical examination, including an assessment for signs suggestive of a potentially immune-mediated medical condition, may be performed, if indicated based on review of interim medical history, by a study clinician licensed to make medical diagnoses and listed on the Form FDA 1572 as the site principal investigator or sub-investigator.
- The second study vaccination site will be examined.
- Approximately 90 mL of venous blood will be collected for cytokine and chemokine levels and systems biology studies.
- Approximately 20 mL of urine will be collected for future research.

**7.2.8 Visit 08, Day 36, Clinic Visit, A/H7N9-vaccinated subjects only
(Window: Day 8+2 days post second study vaccination)**

- Interim medical history, including an assessment for new medical conditions and symptoms suggestive of a potentially immune-mediated medical condition, will be obtained by interview of subjects and any changes since the previous clinic visit or contact will be noted.
- Memory aid information will be reviewed with subjects.
- All concomitant medications (including solicitation for receipt of any non-study influenza vaccines) will be recorded on the appropriate data collection form.
- All AE/SAEs will be recorded on the appropriate data collection form.
- A targeted physical examination, including an assessment for signs suggestive of a potentially immune-mediated medical condition, may be performed, if indicated based on review of interim medical history, by a study clinician licensed to make medical diagnoses and listed on the Form FDA 1572 as the site principal investigator or sub-investigator.
- The second study vaccination site will be examined.
- Approximately 90 mL of venous blood will be collected for cytokine and chemokine levels and systems biology studies.
- Approximately 20 mL of urine will be collected for future research.

**7.2.9 Visit 09, Day 57, Clinic Visit, A/H7N9-vaccinated subjects only
(Window: Day 29±2 days post second study vaccination)**

- Interim medical history, including an assessment for new medical conditions and symptoms suggestive of a potentially immune-mediated medical condition, will be obtained by interview of subjects and any changes since the previous clinic visit or contact will be noted.
- All concomitant medications (including solicitation for receipt of any non-study influenza vaccines) will be recorded on the appropriate data collection form.
- All AE/SAEs will be recorded on the appropriate data collection form.
- A targeted physical examination, including an assessment for signs suggestive of a potentially immune-mediated medical condition, may be performed, if indicated based on review of interim medical history, by a study clinician licensed to make medical diagnoses and listed on the Form FDA 1572 as the site principal investigator or sub-investigator.
- Approximately 10 mL of venous blood will be collected for HAI and Neut antibody assays.

**7.2.10 Visit 10, Day 209, Phone Call/Electronic Communication, A/H7N9-vaccinated subjects only
(Window: Day 181±14 days post second study vaccination)**

Subjects will be contacted by phone or electronic communication (e.g., email, text message) to query for safety events. Adverse events limited to SAEs and MAAEs including new-onset chronic medical conditions and potentially immune-mediated medical conditions that have occurred since the previous clinic visit or contact will be solicited. Based on the information, subjects may be asked to return to the clinic for evaluation.

**7.2.11 Visit 11, Day 394, Phone Call/Electronic Communication, A/H7N9-vaccinated subjects only
(Window: Day 366±14 days post second study vaccination)**

Subjects will be contacted by phone or electronic communication (e.g., email, text message) to query for safety events. Adverse events limited to SAEs and MAAEs including new-onset chronic medical conditions and potentially immune-mediated medical conditions that have

occurred since the previous clinic visit or contact will be solicited. Based on the information, subjects may be asked to return to the clinic for evaluation.

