1. Occurrence of solicited local reactogenicity events within 7 days after each study vaccination.
2. Occurrence of solicited systemic reactogenicity events within 7 days after each study vaccination.
3. Occurrence of unsolicited AEs collected for approximately 28 days after last study vaccination.
4. Occurrence of SAEs and MAAEs including new-onset chronic medical conditions and potentially immune-mediated medical conditions for approximately 1 month (A/H3N2v arm) and 12 months (A/H7N9 arms) after last study vaccination.
5. Number of differentially abundant proteins based on protein abundance as determined by quantitative proteomics in human immune cells at Days 2, 4, and 8 after study vaccination, as compared to baseline assessments (Days -7 and 1) after influenza A/H3N2v vaccine.
6. Number of differentially abundant proteins based on protein abundance as determined by quantitative proteomics analysis, in human immune cells at Days 2, 4, 29, 30, 32, and 36 after study vaccination with AS03-adjuvanted and unadjuvanted A/H7N9 vaccine comparing changes in protein abundance between treatment arms (A/H7N9 vaccine vs. A/H7N9 vaccine + AS03).

Exploratory Objectives

1. To identify and characterize differentially expressed genes in human immune cells on Days 2, 4, and 29 (following the first study vaccination with A/H7N9 vaccine \pm AS03) and on Days 30, 32, and 36 (following the second study vaccination with A/H7N9 vaccine \pm AS03) that differ between treatments (A/H7N9 vaccine vs. A/H7N9 vaccine + AS03).
2. To identify and characterize differentially abundant cellular proteins in human immune cells on Days 2, 4, and 29 (following the first study vaccination with A/H7N9 vaccine \pm AS03) and on Days 30, 32, and 36 (following the second study vaccination with A/H7N9 vaccine \pm AS03) that differ between treatments (A/H7N9 vaccine vs. A/H7N9 vaccine + AS03).
3. To identify and characterize differentially expressed genes in human immune cells on Days 2 and 4 (following the first study vaccination) that differ in baseline responses (Days -7, and 1) between treatments (A/H3N2v vaccine vs. A/H7N9 vaccine and A/H3N2v vaccine vs. A/H7N9 vaccine + AS03).
4. To identify and characterize differentially abundant cellular proteins in human immune cells on Days 2 and 4 (following the first study vaccination) that differ in baseline responses (Days -7, and 1) between treatments (A/H3N2v vaccine vs. A/H7N9 vaccine and A/H3N2v vaccine vs. A/H7N9 vaccine + AS03).

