vaccination). No exceptions to the protocol-specified window will be made. **Note for afebrile, acute illness only:** If a subject is afebrile, his/her acute illness is nearly resolved with only minor residual symptoms remaining, this occurs within the acceptable protocol-specified window for that visit (Day 29±2 days post first study vaccination), and, in the opinion of the site principal investigator or appropriate sub-investigator, the residual symptoms will not interfere with the ability to assess safety parameters as required by the protocol, the subject may receive the second study vaccination without further approval from the DMID Medical Officer. No exceptions to the protocol-specified window will be made.

- Grade 2 or 3 solicited or unsolicited adverse event that is ongoing, whether or not it is improved or resolving. An unresolved or continuing Grade 1 adverse event is permissible following the documented determination by the site principal investigator or appropriate sub-investigator, that it would not render study vaccination unsafe or interfere with the evaluation of responses.
- Grade 3 solicited or unsolicited adverse event that occurs without alternative etiology in the 8 days following the first study vaccination.
- Severe or sustained reaction or disability related to the first study vaccination.
- New onset of illness or condition that meets the Subject Exclusion Criteria (see Section 5.1.2).
- Subject no longer meets eligibility criteria (see Section 5.1). Note: Medication changes subsequent to the first study vaccination are not exclusionary for receipt of the second study vaccination provided there was no deterioration in the subject's chronic medical condition that necessitated a medication change, and there is no additional risk to the subject or interference with the evaluation of responses to study vaccination.
- As deemed necessary by the site principal investigator or appropriate sub-investigator for noncompliance or other reasons.
- Subject refusal of further study vaccination.
- Subject withdrawal of consent.
- Subject lost to follow-up.
- Termination of this study.
- New information becomes available that makes further participation unsafe.

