All subjects will complete a subject memory aid from the time of each study vaccination through 8 days after each study vaccination. Subject memory aids will be reviewed with the subjects for adverse events (solicited injection site and systemic reactions and unsolicited AEs) at follow-up visits occurring through approximately 8 days after each study vaccination.

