 - # Assessment of AE/SAE limited to SAEs and MAAEs including new-onset chronic medical conditions and potentially immune-mediated medical conditions.
 - ** Assessment of AE/SAE limited to SAEs and MAAEs including new-onset chronic medical conditions and potentially immune-mediated medical conditions if after 28 days following the last study vaccination.
 - ² To be performed locally by the site. The ESR value must be confirmed as <30 mm/hr prior to randomization and first study vaccination.
 - ³ A/H3N2v-vaccinated subjects only.
 - Ω Visit 04 is an in-clinic assessment for A/H3N2v-vaccinated subjects and a phone call/electronic communication (e.g., email, text message) assessment for A/H7N9-vaccinated subjects.

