4.5.3. Safety Variables

Safety assessments included:

1. Study vaccine-related serious adverse events occurring from the time of the first study vaccination through approximately 1 month (A/H3N2v arm) and 12 months (A/H7N9 arms) after the last study vaccination.
2. Solicited Adverse Events – reactogenicity events occurring from the time of each study vaccination through 7 days after each study vaccination:
 - a) Injection site reactions including pruritus (itching), ecchymosis (bruising), erythema (redness), induration (hardness)/swelling, pain, and tenderness.
 - b) Systemic reactions including fever, feverishness (chills/shivering/sweating), fatigue (tiredness), malaise (general unwell feeling), myalgia (body aches/muscular pain exclusive of the injection site), arthralgia (joint pain exclusive of the injection site), headache, and nausea.
3. Unsolicited Adverse Events – study vaccine-related non-serious adverse events occurring from the time of each study vaccination through approximately 28 days after each study vaccination.
4. Medically-Attended Adverse Events including new-onset chronic medical conditions and potentially immune-mediated medical conditions occurring from the time of the first study vaccination through approximately 1 month (A/H3N2v arm) and 12 months (A/H7N9 arms) after the last study vaccination.

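### The protocol gives two windows for the A/H7N9 Visit 04 contact. One allows Day 6, and no later review of the dose-1 memory aid is scheduled.

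*Protocol*

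**What the plan says.** **Visit 04 window.** Protocol 7.2.3 (A/H3N2v, clinic) has "Window: Day 8+2 days post first study vaccination". Protocol 7.2.4 (A/H7N9, phone or electronic contact) has Day 8 plus or minus 2 after the first vaccination. Appendix B has one Visit 04 column, headed Day 8 plus 2, and its footnote applies that column to both contact types: "Visit 04 is an in-clinic assessment for A/H3N2v-vaccinated subjects and a phone call/electronic communication" for A/H7N9 subjects. The counterpart after dose 2, Visit 08, has "Window: Day 8+2 days post second study vaccination".

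**Recording and review.** Protocol 8.1 states: "All subjects will complete a subject memory aid from the time of each study vaccination through 8 days after each study vaccination". Review takes place at "follow-up visits occurring through approximately 8 days after each study vaccination". Appendix B marks memory-aid review at V02, V03, V04 and V06 to V08, but not at V05, and the activity list in 7.2.5 has no such item.

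**Use of the period.** Protocol 5.2.3 withholds the second vaccination after a "Grade 3 solicited or unsolicited adverse event that occurs without alternative etiology in the 8 days following the first study vaccination". The reactogenicity halting rules in 9.5 also use 8 days after each vaccination.

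**Length of the period.** The outcome measures in Protocol Section 3 use 7 days ("Occurrence of solicited local reactogenicity events within 7 days after each study vaccination"), and SAP 4.5.3 runs solicited events "through 7 days after each study vaccination". Protocol 8.1, 9.1 and 9.3 use 8 days.

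**The concern.** The window in 7.2.4 contradicts Appendix B for the same contact. Of the contacts that close a memory aid, only the A/H7N9 one after dose 1 may fall before Day 8. If a site follows 7.2.4 and calls on Day 6, the last days of the aid have no scheduled review, and Visit 05 does not supply one.

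Two uses of the data are affected. The first is safety: the dose-2 criterion and the halting counts refer to an 8-day period that may not have been fully reviewed, in arms that include the AS03 arm. Protocol 2.3.1 expects more local and systemic reactions with AS03.

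The second is analysis. SAP 10.2.1 tabulates solicited events by day and by maximum severity over 7 days, with subjects who have non-missing data for the event as the denominator. SAP Listings 10 and 11 describe memory-aid data as reviewed by clinic staff before entry. A subject reviewed only to Day 6 could stay in the denominator with a maximum taken over fewer days.

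**Working it through.** The plan states no figure for this point, so there is none to reproduce. The check is day counting.

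**Inputs.** Vaccination is Day 1 (Appendix B). Permitted contact days: 6 to 10 under 7.2.4; 8 to 10 under Appendix B, under 7.2.3, and for Visit 08 counted from dose 2. The last day of the solicited period is Day 8 if it means 7 days after Day 1 (1 + 7), or Day 9 if it means literally 8 days after (1 + 8).

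**Formula.** Days without scheduled review = max(0, last day of period − day of contact), counting the day of contact as reviewed.

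| Setting | Earliest contact | Period ends Day 8 | Period ends Day 9 |
|---|---|---|---|
| A/H7N9, dose 1, per 7.2.4 | Day 6 | 8 − 6 = 2 | 9 − 6 = 3 |
| A/H7N9, dose 1, per Appendix B | Day 8 | 8 − 8 = 0 | 9 − 8 = 1 |
| A/H3N2v, per 7.2.3 | Day 8 | 0 | 1 |
| A/H7N9, dose 2, Visit 08 | Day 8 | 0 | 1 |

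A contact on Day 10 leaves 0 days in every row. At worst, 2 of 8 days (25%) or 3 of 9 days lack scheduled review. The excess of 7.2.4 over the other settings is 2 days on either reading (2 − 0, or 3 − 1).

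**Subjects exposed.** Two A/H7N9 arms of 10 give 20 subjects, after dose 1.

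**Halting threshold.** Protocol 9.5 requires 10% or more of all subjects dosed to date, with a minimum of 2, to have the same related Grade 3 reaction. The threshold is max(2, ceiling of 0.10 × N): 2 subjects for N up to 20, and 3 for N from 21 to 30. One event cannot meet the rule alone, but one late-reported event can decide whether a count stands at the threshold.

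**Possible delay.** A reaction on Day 8 first recorded at Day 29 is 29 − 8 = 21 days late. Over Days 7 to 9 and the Visit 05 window (Day 27 to 31), the range is 27 − 9 = 18 to 31 − 7 = 24 days.

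**The case against.** A reader might infer that late Grade 3 reactions would simply be lost in the A/H7N9 arms, so that subjects receive dose 2 when they should not. The documents do not support that.

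- Under 7.1.2 subjects are told on Day 1 to notify the center of severe reactions, the grade at issue here.
- Before dose 2, Section 7.2.5 requires an eligibility review, an interim history since the last contact, and recording of all adverse events. Appendix B marks the Visit 05 adverse event assessment as including reactogenicity through 8 days.
- Protocol 5.2.3 also withholds dose 2 for a severe or sustained related reaction, and for an ongoing Grade 2 or 3 event. Neither is tied to the 8-day period.
- Nothing says that the aid is handed in, or that recording stops, at the call. Recall on Day 29 need not be unaided.

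A reader might also infer that one missed event, being 10% of an arm of 10, would decide a halt. The halting denominator is all dosed subjects, with a minimum of 2. Nor is the gap strictly confined to the A/H7N9 arms: on the literal 8-day reading a Day 8 visit is one day early elsewhere too.

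Finally, it is too strong to call the dose-1 solicited rates non-comparable. Protocol 2.3.1 says of unadjuvanted licensed vaccines that most reactions peak within 24 hours, and the Visit 02 and 03 reviews (Days 2 and 4) are the same in all arms. Solicited events are a tertiary outcome in a hypothesis-generating study.

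These points limit the consequence. They do not remove the contradiction between 7.2.4 and Appendix B or the missing review at Visit 05. General adverse event recording on Day 29 is not a day-by-day review of the aid.

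**Conclusion.** The point holds as a contradiction in the visit window combined with a gap in scheduled review. Under 7.2.4, 2 days of the dose-1 memory aid (3 on the literal reading, against 1 in the other settings) can go without scheduled review in any of the 20 A/H7N9 subjects. The result is incomplete daily solicited data and delayed or recall-based capture, about three weeks late for the halting counts. Certain loss of events is not shown, and few events are expected.

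The size assumes that sites use the early edge of the 7.2.4 window. If Appendix B governs, the Day 6 case disappears, but Visit 05 still has no review and the literal reading still leaves one day. The documents do not say which window takes precedence.

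**What to change.** 1. Reconcile the Visit 04 window in Protocol 7.2.4 with Appendix B.
2. Reconcile the 7-day solicited period (Protocol Section 3, SAP 4.5.3 and 10.2.1) with the 8-day period (Protocol 8.1, 9.1 and 9.3), and state the last day as a study day. Taken together, the reconciled texts should ensure that the last scheduled review covers the whole solicited period.
3. Add review or collection of the completed dose-1 memory aid for A/H7N9 subjects at Visit 05, in 7.2.5 and Appendix B, before the second-vaccination criteria are checked.

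The dose-2 and halting criteria are not changed. The cost is a wording correction and one review item at an existing clinic visit. If the windows are aligned to Appendix B, the call also loses its two early days of flexibility (Days 6 and 7).
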